dangerously high. If participants decline to have 911 called, they will be required to sign a waiver indicating this decision. Participants will be advised to seek medical care immediately. Research Electronic Data Capture (REDCap), a secure, HIPAA-compliant web application for managing online surveys and databases, will be used to administer questionnaires. For participants who are eligible, study staff will describe the study and obtain informed consent. Participants will complete questionnaires on a laptop/tablet device, provide anthropometric measures, complete the fitness measures. Anthropometric measures include measured height, weight, waist circumference, and percent body fat. Height and weight will be measured using a stadiometer and digital scale, respectively. During the baseline assessment, study staff will work with participants to create a Fitbit account.

Process Evaluation. Process evaluation will be used to monitor and document program implementation via assessment of intervention dose (amount of intervention delivered and received), reach (extent of intervention participation by the target population), and fidelity (extent to which the intervention was implemented as planned). For dose, we will track the extent to which coaching session was completed, intended content was covered, and newsletters were received and read. Reach will be assessed by tracking participation of dyad members for each session (0, 1, or both) along with barriers to participation, dyad interaction, and use of the Fitbit, including frequency of monitoring partner's PA. Individual participants' Fitbit data from Fitabase dashboard will be used by intervention coaches to review participants' data and aid them with providing feedback. We will also use this information to evaluate participants' adherence to self-monitoring. To assess fidelity, all coaching sessions will be digitally recorded. Holistic nurse health coach will be required to keep detailed implementation logs showing the date and start and end times of sessions, individuals present, the content discussed, goals set by participants that will be followed up on the next session, dyad support plans, and any qualitative observations.

Measures: Surveys will be administered using Research Electronic Data Capture (REDCap), a secure, HIPAA- compliant web application. Table 1 (Appendix-D) shows the schedule of study procedures and constructs to be assessed, proposed measures, and the timing of assessment.

Physical Activity. Fitbit data include daily step counts, floors climbed, activity intensity, heart rate, and sleep data along with wear/usage data. If participants do not wear the Fitbit as recommended, this will not be recorded as a deviation Fitbit data will be PA will be described in terms of step count per minutes and total minutes being in moderate, and vigorous PA. Self-reported PA will be assessed with the Godin Leisure Time Exercise Questionnaire,⁹⁴ which assesses episodes, intensity, and duration of PA during a typical 7-day period. Good test-retest reliability has been observed, with test-retest correlation coefficients ranging from 0.48 for light activity to 0.94 for strenuous activity.⁹⁴

Anthropometry. Non-fasting weight in light clothing, height without shoes, waist (at the iliac crest) circumference, and percent body fat will be measured by trained staff. Measurements will be assessed in duplicate or until two measurements are within the permitted variance (weight, 0.2 kg; height and waist circumference 0.3 cm) using a calibrated digital floor scale, a stadiometer, and a Gulick tape measure with a 6 oz. tension meter. Percent body fat is assessed using the digital Tanita scale.

Blood Pressure (BP). Participants will have their BP taken by a trained staff member with an arm blood pressure monitor. Participants will be provided with a written recording of their

blood pressure and will be referred to the information sheet (see “Participant Measures and BP Report”) regarding recommendations. Participants with elevated and high blood pressure ($\geq 120/80$ mm Hg), as defined by the 2017 American College of Cardiology and American Heart Association, will be encouraged to see a healthcare provider. Participants who do not have a regular healthcare provider will be provided with a list of low-cost clinics in Harris County. Participants with BP readings $\geq 180/120$ mm Hg will be informed that study staff must contact 911 due to their BP being dangerously high. If participants decline to have 911 called, they will be required to sign a waiver indicating this decision. Participants will be advised to seek emergency care or follow up with their healthcare provider immediately.

Questionnaires. Questionnaires to be completed by participants are listed in Table 2 (Appendix-E) and briefly described below. REDCap (Research Electronic Data Capture) will be used to administer questionnaires.

Screening

- The *Physical Activity Readiness Questionnaire (PAR-Q)* is a pre-activity screening tool recommended by the American College of Sports Medicine as a minimal standard for entry into low and moderate intensity exercise programs.⁹⁵ The PAR-Q serves to identify individuals who should consult a medical practitioner prior to participation in an exercise program.
- *The Godin Leisure Time Exercise Questionnaire*⁹⁴ assesses episodes, intensity, and duration of PA during a typical 7-day period. Good test-retest reliability has been observed, with test-retest correlation coefficients ranging from .48 for light activity to 0.94 for strenuous activity.⁹⁴ Other studies have confirmed reliability and validity,⁹⁶ and this measure has been validated with accelerometers.⁹⁷

Demographics and Health

- *Demographic characteristics* are drawn from the Behavioral Risk Factor Surveillance System and will include variables such as participants’ age, gender, race/ethnicity, country of birth, marital status, highest level of education, current employment status, and household income.
- Chew’s one-item *Health Literacy Screening Question*⁹⁸ assesses individuals’ self-reported ability to perform health literacy-related tasks. Participants respond to one question on a 5-point Likert scale (scores range from 1 to 5). Several studies have found that the question "How confident are you filling out medical forms by yourself" has the greatest accuracy in identifying individuals with limited and marginal health literacy.^{99,100}
- *Self-Rated Health* is a one-item measure that asks participants to rate their health on a continuum ranging from excellent to poor. Self-rated health has been shown to be a consistent predictor of mortality in diverse populations and sensitive to health indicators and social factors.¹⁰¹
- *Health History* is a one-item measure that asks participants to indicate whether they have had specific medical problems in the past 12 months. These medical problems include diabetes, cancer, high blood pressure or cholesterol, stroke, asthma, thyroid problems, and heart, kidney, or lung disease.

- *Online Access* questions from the Pew Research Center assess the ways in which participants access the internet.
- *Value Assessment*: At the baseline assessment, we will ask participants about their top three *values* from a pre-selected list of 22 values (e.g., good parent, responsible, caring). These values will be provided to the health coaches to inform the health coaching sessions.

Social Context

- The *Interpersonal Support Evaluation List* (ISEL-12) is a 12-item measure of perceived social support overall and within three dimensions: appraisal support, belonging support, and tangible support. The ISEL-12 and its subscales have demonstrated adequate test-retest reliability and internal consistency, and good convergent and criterion validity.¹⁰²
- The *Social Support* measure for PA assess family and friend social support specific to exercise behaviors.¹⁰³ These scales exhibit good reliability (e.g., $\alpha=0.83$) and have been used with minority populations.^{57,104}
- *Important Others Climate Questionnaire (IOCQ; Autonomy Support)* measures the perception of the autonomy supportiveness of an “important other” with respect to an identified behavior.¹⁰⁵ In this study, we will assess perceived autonomy supportiveness of the study partner from the perspective of the participant, and the perceived autonomy supportiveness provided by the study participant to her study partner.
- *Partner Characteristics and Relationship Quality*: We propose to ask a series of questions to collect information on participants’ study partners and to characterize the relationship between dyad members. This includes such information as the type of relation, frequency of interaction, strength of relationship, and content and format of communication. These questions were adapted from egocentric questions.¹⁰⁶ Overall *relationship quality* will be assessed with a global rating item from the National Survey of Families and Households, with response options ranging from 1 (poor) to 5 (excellent).

PA-related Measures

- *Self-efficacy for PA* assesses confidence in one’s ability to be physically active on a regular basis in the face of various barriers. This construct is one of the most consistent correlates of PA behavior in diverse samples of adults.¹⁰⁷
- The *Stage of Change* questionnaires for PA consists of 2 questions assessing readiness to engage regularly in PA,¹⁰⁸⁻¹¹⁰ Participants can be classified into one of five stages of change: pre-contemplation, contemplation, preparation, action, and maintenance. Concurrent validity tests indicate strong validity evidence for this staging measure.¹¹¹

- The *Behavioral Regulation in Exercise (BREQ-3)* questionnaire assesses motivation to exercise. The questionnaire contains 24 items within six subscales, all of which have acceptable internal reliability ($\alpha=0.73-0.86$).¹¹²

Physical Activity Outcomes

- *The Godin Leisure Time Exercise Questionnaire*⁹⁴ assesses episodes, intensity, and duration of PA during a typical 7-day period. Good test-retest reliability has been observed, with test-retest correlation coefficients ranging from .48 for light activity to 0.94 for strenuous activity.⁹⁴ Other studies have confirmed reliability and validity,⁹⁶ and this measure has been validated with accelerometers.⁹⁷
- The *Multi-Context Sitting Time Questionnaire* (MSTQ) assesses time spent sitting on both work and non-work days.¹¹⁴ The MSTQ assesses common sedentary behaviors such as watching television, computer use, reading, socializing, and transport. Intraclass coefficients for the MSTQ demonstrated acceptable reliability (ICCs >0.70), and the MSTQ performed similarly to other measures of sedentary behavior.

Other Behaviors

- We will assess diet using items from the BRFSS. Six items assess fruit and vegetable intake.
- We will also assess Cognitive function using Montreal Cognitive Assessment: MoCA Version 7.1 (Original Version)¹¹⁵(Appendix-E). The MoCA is a screening test assessing global cognitive function that assesses memory, visuospatial ability, executive function, attention, concentration, working memory and orientation. This can be used for screening for mild cognitive impairment (MCI). The MoCA takes approximately 10 minutes to administer. The total possible score is 30 points with a score of 26 or more considered normal. To better adjust the MoCA for lower educated individuals, 2 points should be added to the total MoCA score for those with 4-9 years of education and 1 point for 10-12 years of education. The score range for MCI is 19-25.2 and for Alzheimer's dementia. The MoCA detected MCI with 90%-96% range sensitivity and specificity of 87% with 95% confidence interval. The MoCA detected 100% of Alzheimer's dementia with a specificity of 87%¹¹⁶. A trained research assistant who has successfully completed official MoCA training and certification module will administer this test.

Ethics

The study team will get approval from the Committee for the Protection of Human Subjects (CPHS) at the University of Texas Health Science Center at Houston before the recruitment of study participants. Potential participants will be informed regarding the overall goals of the study and stated that the data collected will remain confidential, and used strictly for research purposes and will get an informed consent (Appendix-C).

Potential Challenges and Risks and Procedures for Minimizing Risks

Risks associated with study participation are minimal as all data collection is non-invasive and

primarily non-personal. Minimal risk is defined as the probability and magnitude of physical or psychological harm that does not exceed that encountered in ordinary, everyday life or in the performance of routine medical or psychological examinations. Risks include: becoming fatigued when participating in sessions, feeling uncomfortable interacting with the study team during sessions, and breach of confidentiality. Participants will be notified of these risks during the informed consent process. If any concerns arise during study procedures, participants will be reminded that participation is voluntary and they may refuse to answer any questions, end the session, or withdraw from the study at any time without fear of repercussion. If a participant is too tired or ill to continue with a scheduled session, the session will be ended and if (and only if) the participant is willing and able the session will be rescheduled. All attempts possible will be made to minimize the risk that a participant's data will become known to others outside the approved research team (see Data Management). The research team will ensure the anonymity of the participants by protecting personally identifiable information. The proposed study will be conducted in English; India is a linguistically diverse country with 22 languages recognized by the constitution of India¹¹⁷ and it is not feasible to conduct focus groups in multiple languages. However, English is also considered a popular second language in India¹¹⁸ and is used as the language for communication in U.S. Asian Indians speak English very well (57.7%)¹¹⁷ and limited English proficiency is fairly low (7.3%) and are bilingual since they speak another language at home¹¹⁷.

Height/Weight/Waistline Measurements

Having weight or waistline measurements taken may make participants feel uncomfortable. Participants may refuse to complete any procedure that makes them feel uncomfortable.

Physical Activity Side Effects

This study encourages increased participation in physical activity of a moderate nature. This activity may result in mild physical discomfort (e.g., sore muscles, stiffness) for some participants. These effects have no long-term negative health implications and are a normal consequence of activity. However, more serious potential risks include pulled muscles, heart problems, chest tightness or discomfort, shortness of breath, and accidental injuries, such as falling. Possible outcomes could include referral to the participant's primary care physician and/or other physician. Our inclusion/exclusion criteria were designed to exclude participants who should not participate in regular light-to-moderate physical activity based on their responses to the PAR-Q and blood pressure measures without the authorization of a healthcare provider.

Study Withdrawal/Discontinuation

Participants may withdraw from this study at any point in time without repercussion, by simply indicating their desire to withdraw to a study team member.

Criteria for Removal from the Study:

- Participant or clinician request
- Inability to contact the patient for 1 month (up to 6 attempts will be made)
- Completion of study
- Study team determined the patient was no longer eligible

- Sessions were not productive
- Deceased
- Health status declined

All data captured from withdrawn participants will be considered evaluable and used for this study, unless a withdrawn participant requests to have their data destroyed.

Data and Safety Monitoring

Study team members will continuously monitor participant safety and data quality whenever conducting study activities. Study personnel will maintain quality assurance procedures for all data. Survey data will be collected and managed using REDCap (Research Electronic Data Capture). All protected health information (PHI) will be removed from the data when it is exported from REDCap for analysis. Those having access to the data file include the study Principal Investigator (PI) and research team personnel and will monitor recruitment, data quality, data management, and human subjects' protection at least bi-weekly. Logs will be maintained of refusals during recruitment, any participant complaints, and other adverse events and will be reported according to Institution Review Board (IRB) requirements. [name] will work to address and resolve any concerns in the most expeditious manner possible. In particular, participant responses to recruitment attempts will be tracked in terms of methods of contact, and reasons for refusal (if available) and contact attempts made by the study team. This information will be reviewed on a bi-weekly basis, and if any concerning trends are noted in recruitment refusals, the IRBs will be notified and adjustments made to recruitment strategies and / or study procedures (as indicated).

Several procedures will be used to maintain the integrity of the data. Quality assurance procedures will include a data collection protocol documented in a protocol manual, and regular meetings among the investigators and project staff to review problems and solutions and discuss concerns. A specific audit trail system that identifies the date, time, and individual making changes on the database will be part of the data management system.

No protected health information will be included in the text/email messages (as there will be no health information in the message). Although participants' phone numbers and the content of the text messages will be disclosed to the automated text messaging service, no protected health information will be disclosed to the automated text messaging service. Participants will be informed that unencrypted text and email messages are not secure and may choose not to receive them.

To minimize the possibility of a breach in confidentiality, data for this study will only be accessible by study team members. Communication with participants may occur in-person or via electronic mail or telephone calls. Voice mails left for participants will contain just the information necessary to return the contact (no identifiable or confidential information). Only UTHealth or site institutional email addresses will be used to communicate with participants.

Data Handling and Record Keeping

Identifiable participant data will be kept in secure locked areas at the Cizik School of Nursing or in password-protected electronic files accessible only by study staff. All identifiable electronic

data (including original recordings and participant contact information) will be stored and managed in a secure, password-protected folder on a server approved for the storage of protected health information or in a secured Research Electronic Data Capture (REDCap™) database, per UTHealth policy. Participants' names and identifiers will be linked to the study identification number in a database that will be password protected, with access restricted to the PI and designated research staff. Paper records (e.g., signed ICDs, completed screening forms) will be kept in a locked file room. All signed informed consent documents and/or HIPAA authorizations will be securely maintained for at least 6 years after the close of the study. Recruitment data will be stored separately from the data of participants who enroll in the study. In particular, a full list will be maintained of participant responses to recruitment attempts by site study team members on a secured and password-protected server managed by that site.

[name], statistician of the study, will have access to identifiers needed for analysis such as date of birth (to calculate age) and assessment dates. Other collaborators will have access to de-identified data only. Participants' residential addresses will be collected to access publicly available information about the area in which participants live. This can help us understand how their neighborhood is conducive to physical activity. Results from data analyses using this information will only be reported in aggregate form, and no participants will be identifiable from any research products resulting from this protocol. Participants' residential addresses will never be released/published in any form (e.g., maps, graphs/charts). Addresses will be stored separately from other study data, and following the procurement of neighborhood information, access to participants' addresses will be limited to the PI. Although every effort will be made to keep study data safe, there is a chance that personal health information could be lost or stolen.

After the research described here is complete and the manuscript/s written, access to the de-identified data files will be limited to the PI and research staff/collaborators, who will maintain the files on the institutional server in case any questions emerge from peers or regulatory agencies regarding the resulting publications. Recordings of coaching sessions will be deleted following the completion of analysis. Following study termination, data and identifiers will be handled as per applicable policies and regulations.

Statistics

The feasibility of the intervention will be determined by comparing the percentages for overall recruitment and retention at week 12 to their target values of 80% and 70%, respectively. A secondary feasibility assessment will determine the proportion of intervention participants who take part in each of the intervention components (i.e., number of counseling calls completed, use of Fitbit, receipt and review of newsletters). In addition, every attempt will be made to query subjects lost to follow-up to ascertain the reason for drop out or barriers to participation. Feasibility will be measured by calculating the rates of enrollment, retention, assessment completion, and treatment adherence. The enrollment rate will be the proportion of those meeting inclusion criteria that enrolled, while the retention rate will be the proportion enrolled that complete the study. Assessment completion will be calculated as the proportion of assigned data collection forms that were completed. Treatment adherence will be calculated as the proportion of intervention sessions attended.

To explore trends in the outcomes data, means and standard deviations will be calculated for the instrument scores at baseline and week 12. As hypothesis testing is not the objective of a pilot

study¹¹⁸, these descriptive statistics will only be used to inform effect size estimation. Since the effect sizes in a pilot study may overestimate or underestimate the true effect sizes¹²⁰ the obtained effect size estimates will be considered in combination with clinically significant effect sizes for the outcome variables in determining the sample size for a future trial.

Power Analysis: The primary aims do not require power calculations given the focus on feasibility study.

Anticipated Results: This study will provide the foundation for further large-scale efficacy testing of the dyadic social support PA intervention with the ultimate goal of improving the health and well-being of SAI women. The proposed intervention also integrates cultural values and norms into aspects of the design and delivery to enhance intervention relevance, appeal, and engagement of PA to yield long-term positive impact on the health of SAI women. The results of the study will be published in the scientific journals in a manner that will be accessible to other academic institutions and researchers. We also plan to model with SAI community organizations and health clinics that serve this population and would benefit from the study's outcomes largely. Our project is timely and urgent for at risk SAIs women as it can improve PA to build healthy new habits that last a lifetime. Moreover, the nurse coach will help you learn new skills, encourage to set and meet goals, and keep motivated. Moreover, dyad partners can share ideas, celebrate successes, and work to overcome obstacles. Our study is related to current national priorities. The major goal of Healthy People 2030 is to reduce health disparities among racial and minority groups especially SAIs and to reduce obesity and diabetes by promoting physical activity. The National Institute of Health also encourages investigator-initiated research on minority health and health disparities.

Publication Plans

We will submit abstracts of the study findings for presentation at the conferences of Society of Behavioral Medicine and American Heart Association and plan to submit a manuscript for publication in *the American Journal of Public Health and Journal Preventive Medicine Reports* as second choice.

Potential for Extramural Funding

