The proposed single-arm pilot study will test the feasibility of recruitment, retention, acceptability and implementation of study procedures of a 12-week dyadic behavioral intervention to promote positive and sustained change in MVPA, social support, and self-efficacy among inactive SAI women in Houston, TX. The intervention will target 10 dyads of inactive SAI women and will include dyad-based Zoom coaching delivered by a certified holistic nurse coach using a motivational interviewing approach to promote social support between dyad members as they practice how to be supportive partners; employing a Fitbit device to monitor one's own and one's exercise partner's PA; and dissemination of PA-related health education.

Study Population and Eligibility

For this study, participants will be SAI women aged 40-65 years living in Houston, Texas; insufficiently active (PA<150 minutes/week); physically able to engage in moderate PA; speak and read English; able to enroll with an eligible adult female partner who does not live in the same household; willing to use the Fitbit app/device; own a smartphone that is compatible with Fitbit software (up to 223.3 MB on iPhone or 165 MB on Android) 9); able and willing to send and receive text messages; and Blood pressure reading <160/100 mm Hg, or with medical clearance. Exclusion criteria include SAI women with a current/planned pregnancy; cannot speak and read English, those participating in a PA or weight loss program, and those diagnosed with a physical disability that interferes with their ability to be physically active.

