Data collection and study procedures are shown in Table 1 (Appendix -D). Data collection will take place at baseline and immediately post-intervention (approximately 3-months after baseline). Each participant will be compensated for their time with \$40 (at baseline) and \$50 (at 12-week follow-up) in gift cards upon completing study procedures and parking (as needed) for each visit.

All participants will also be provided with a Fitbit device that will enable participants to monitor their own and their partner’s PA, and will also allow research staff and the nurse health coaches to monitor participants’ PA. Data collection will be conducted in-person by UTHealth staff (research assistant) at community sites (e.g., Indian community center, churches, other religious organizations, health fairs, and health screenings targeting Asian Indians in Houston etc.) depending on participants’ preference.

At baseline study staff will first request permission to take participants’ blood pressure to confirm eligibility. Following the measurement, all participants will be provided with health education on blood pressure. Participants with elevated and high blood pressure ($\geq 120/80$ mm Hg), as defined by the 2017 American College of Cardiology and American Heart Association, will be encouraged to see a healthcare provider. Participants with BP readings $\geq 160/100$ mm Hg will be informed that they can participate in the study only with a letter from a healthcare provider clearing them for participation. If participants do not have a healthcare provider, a list of low-cost clinics in Harris County will be provided. Participants with pressure readings $\geq 180/120$ mm Hg will be informed that study staff must contact 911 due to their BP being

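### Unproductive coaching sessions are listed as a ground for leaving the study, not just coaching, which on the natural reading could cost retention and week-12 data (minor)

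*Combined protocol and SAP*

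**What the plan says.** The removal criteria under *Study Withdrawal/Discontinuation* include "Sessions were not productive". This entry stands apart from those for a request by the participant or a clinician, one month without contact, and declining health. Another entry reads "Study team determined the patient was no longer eligible". The section then states: "All data captured from withdrawn participants will be considered evaluable and used for this study", unless a withdrawn woman asks for her data to be destroyed.

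Where the woman herself decides, *Potential Challenges and Risks and Procedures for Minimizing Risks* separates the levels: "they may refuse to answer any questions, end the session, or withdraw from the study at any time". The removal list makes no such separation for unproductive sessions.

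On measurement, *Statistics* compares week-12 retention with a 70% target and says "the retention rate will be the proportion enrolled that complete the study". It has a separate measure for sessions: "Treatment adherence will be calculated as the proportion of intervention sessions attended". *Study Design* gives the size: "The intervention will target 10 dyads of inactive SAI women". *Data Collection and Study Procedures* plans two assessments, at baseline and about three months later. The abstract places the open-ended satisfaction evaluation at the follow-up.

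**The concern.** Retention is one of two feasibility measures with a numerical target, and it should show whether women stay. If poor coaching sessions end study participation, the rate mixes the team's stops with women's own decisions to leave. Treatment adherence already exists to show how coaching went.

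The loss would also be related to outcome. The women affected are those whose coaching went badly, and their week-12 Fitbit value, questionnaires, measurements and satisfaction form are what would be missing. Acceptability is part of the study hypothesis, so their views matter. The week-12 means, which feed effect-size estimates for a later trial, would lean towards women for whom coaching worked, although that effect is likely small.

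**Working it through.** **Inputs from the protocol.** 10 dyads, so 20 women; retention target 70% at week 12; retention = completers / enrolled; 6 sessions per dyad; $50 gift card at week 12. The protocol states no power, sample-size or drop-out figure to reproduce.

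**Inputs assumed.** The number of women removed on this ground (k), the completion probability of the others (p), and the probability that removed women would have completed if kept in follow-up (q). None of these is in the protocol.

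**Target as a count.** 0.70 × 20 = 14 completers, so at most 6 losses from any cause. 14/20 = 70% meets the target; 13/20 = 65% misses it.

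**Cost per removal of a woman who would have completed.** 1/20 = 5 points. If both members of such a dyad are removed, 2/20 = 10 points and 2 of the 6 allowed losses.

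**Chance of reaching 14, women treated as independent, p = 0.80.** Removed: P(Bin(20−k, 0.80) ≥ 14). Kept in follow-up: P(Bin(20−k, 0.80) + Bin(k, q) ≥ 14).

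| Removed (k) | As written | Kept, q = 0.4 | Kept, q = 0.8 |
|---|---|---|---|
| 1 woman | 0.837 | 0.875 | 0.913 |
| 2 (one dyad) | 0.716 | 0.826 | 0.913 |
| 4 (two dyads) | 0.352 | 0.694 | 0.913 |

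With k = 0 nothing changes.

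**Sensitivity to p, with q = p and k = 2.** The chance moves from 0.608 to 0.333 at p = 0.70, from 0.786 to 0.519 at 0.75, from 0.978 to 0.879 at 0.85, and from 0.998 to 0.972 at 0.90.

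**Dyads that stay or leave together.** The target becomes 7 of 10 dyads. With one dyad removed, P(Bin(9, 0.80) ≥ 7) = 0.738. If that dyad is kept and completes with probability 0.80, the chance is P(Bin(10, 0.80) ≥ 7) = 0.879. If it completes with probability 0.4, the chance is 0.738 + 0.4 × P(Bin(9, 0.80) = 6) = 0.738 + 0.4 × 0.176 = 0.81. The gap is therefore 0.07 to 0.14, depending on q.

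**Where poor coaching would show instead.** A dyad stopped after session 3 misses 2 × 3 = 6 of 20 × 6 = 120 planned woman-sessions, which lowers adherence by 5 points.

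**The case against.** The list is loosely drafted. It includes finishing the study and death, which are not decisions to remove anyone, so it may only record how participation ended. That is fair, and it means the protocol does not clearly announce a policy of removing willing women. But on either reading participation ends on this ground, and no stop-coaching-only category appears.

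Counting such women as not retained is defensible in a pilot, since coaching that cannot be made productive is itself a feasibility finding. This stands as a legitimate choice, and it is why the fix must keep coaching stops visible. It does not justify losing the week-12 data.

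The protocol also makes such removals less likely. Goals and support plans are revised at each meeting, the coach contacts women individually, and sessions can be rescheduled. Attrition reasons are tracked, so a missed target could be explained afterwards. The comparison with 70% is descriptive, and the larger figures above need several removals that nothing in the protocol suggests. All of this stands and keeps the point small.

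Four stronger readings are tempting and not supported:
- A reader might infer that the plan says removed women count against retention. It does not; that follows from the natural meaning of completing the study, which is not defined further.
- A reader might infer that nothing anywhere provides for their week-12 data. Appendices C and D and the protocol manual are unavailable and could do so.
- A reader might take the lack of a definition or named decision maker as the fault. That is missing detail, and the health-decline entry names no one either.
- A reader might assume that both partners leave. The protocol does not say so, and *Process Evaluation* foresees sessions attended by one member.

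**Conclusion.** The point holds in a modest form and is minor: a cheap improvement. As written, unproductive sessions can take a willing woman out of the study before her only post-intervention assessment. On the natural reading of the retention definition, that costs 5 points, or 10 for a dyad, where those women would otherwise have completed, and loses their week-12 measures and satisfaction form. The effect depends entirely on a removal rate that is not stated and may be zero; the probabilities shown are illustrations under assumed completion rates. Baseline data, Fitbit data up to removal, session logs, coach notes and attrition reasons are kept, so much of the process evidence survives.

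**What to change.** Make unproductive sessions a reason to stop coaching only. Still invite every such woman who has not withdrawn consent to the planned week-12 visit and satisfaction form. Keep all enrolled women in the retention denominator. So that retention is not flattered, report team-initiated coaching stops in a row separate from participant-initiated drop-out, and calculate adherence over all 6 planned sessions for every enrolled woman. While the line is being edited, it would be sensible to say who decides and whether the stop applies to one woman or the dyad, but that alone would not address the point. Clinical grounds for stopping coaching stay with the investigator.

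The cost is a wording change, one table row and a few visits already planned for every enrolled woman. At $50 each that is $100 for one dyad (2 × $50) or $200 for two (4 × $50), plus staff time and parking as needed.
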